### 8.11.3. Visit 3 (Dose 3 Visit, 4 to 8 Weeks After Visit 2[Dose 2])

- Ensure and document that the participant continues to be eligible for the study (see [Section 7.2](#) for participant discontinuation/withdrawal) and none of the temporary delay criteria are met ([Section 5.5](#)).
- Record nonstudy vaccinations administered since Visit 2, as described in [Section 6.5](#).
- Review the participant's e-diary data with the participant's parent(s)/legal guardian(s); collect stop dates of any e-diary events ongoing on the last day that the e-diary was completed and record stop dates in the CRF.
- Determine whether any AEs (includes nonserious AEs, SAEs, and NDCMCs) have occurred since the previous visit and follow up on any previously reported events to determine the outcome (ie, record stop dates or confirm if they are still continuing) and record as described in [Section 10.3](#), and record concomitant medications used to treat NDCMCs and SAEs.
- Measure and record the participant's axillary temperature (°C).
- Unblinded site staff will administer a single 0.5-mL injection of 20vPnC or 13vPnC into the anterolateral thigh (preferably into the left anterolateral thigh). (NOTE: A **blinded** site staff **should not** open a carton of the investigational product in order to maintain the blind).
- The site staff (either blinded or unblinded) will administer concomitant vaccines containing diphtheria, tetanus, acellular pertussis, poliovirus, and Hib and rotavirus antigens and other permitted vaccines into the upper arm(s) or orally (in the case of rotavirus vaccine). A blinded staff member will record the site of administration on the CRF.

After vaccination:

- Blinded site staff will observe the participant for 30 minutes after vaccination for any reactions.
- Record any AEs on the CRF and on an SAE form as applicable. Record concomitant medications used to treat SAEs and NDCMCs.
- Confirm that the e-diary is working and review instructions if necessary. Remind the participant's parent(s)/legal guardian(s) to complete the e-diary from Day 1 to Day 7, with Day 1 being the day of vaccination. Provide a thermometer or measuring device if needed.
- Ask the participant's parent(s)/legal guardian(s) to contact the investigator site staff or investigator as soon as possible during the 7-day postvaccination period if the participant has a fever  $>40.0^{\circ}\text{C}$ , redness and/or swelling at the 20vPnC or 13vPnC injection site measuring  $>14$  measuring device units ( $>7$  cm), or severe 20vPnC or 13vPnC injection site pain (causes limitation of limb movement), to determine if the event requires further assessment by the investigator.
- Remind the participant's parent(s)/legal guardian(s) to contact the investigator or investigator site staff as soon as possible if any significant illness or medical event (eg, emergency room visit or hospitalization) occurs during the study period.
- Confirm whether the participant's parent(s)/legal guardian(s) still possesses the participant contact card. Provide a participant contact card if needed.
- Remind the participant's parent(s)/legal guardian(s) that the use of prophylactic antipyretic/pain medication, while permitted, is not recommended on the day of investigational product administration (before or after vaccination).
- The investigator or an authorized designee completes the CRF and the source documents and updates the investigational product accountability records.
- The investigator or appropriately qualified designee reviews the e-diary data online at frequent intervals for the 7 days following vaccination to evaluate participant compliance and as part of the ongoing safety review.

**8.11.4. Visit 4 (Dose 3 Follow-up Visit, 28 to 42 Days After Visit 3 [Dose 3])**

- Ensure and document that the participant continues to be eligible for the study (see [Section 7.2](#) for participant discontinuation/withdrawal) and none of the temporary delay criteria are met ([Section 5.5](#)).
- Record nonstudy vaccinations administered since Visit 3, as described in [Section 6.5](#).

- Review the participant's e-diary data with the participant's parent(s)/legal guardian(s); collect stop dates of any e-diary events ongoing on the last day that the e-diary was completed and record stop dates in the CRF.
- Collect the e-diary (if applicable).
- Determine whether any AEs (includes nonserious AEs, SAEs, and NDCMCs) have occurred since the previous visit and follow up on any previously reported events to determine the outcome (ie, record stop dates or confirm if they are still continuing) and record as described in [Section 10.3](#), and record concomitant medications used to treat NDCMCs and SAEs.
- Collect a blood sample of approximately 5 mL for immunogenicity (a topical anesthetic is permitted).
- The investigator or an authorized designee completes the CRF and the source documents.

#### 8.11.5. Visit 5 (Dose 4 Visit, 12 to 15 Months of Age)

- Ensure and document that the participant continues to be eligible for the study (see [Section 7.2](#) for participant discontinuation/withdrawal) and none of the temporary delay criteria are met ([Section 5.5](#)).
- Record nonstudy vaccinations administered since Visit 4, as described in [Section 6.5](#).
- Determine whether any SAEs or NDCMCs have occurred since the previous visit and follow up on any previously reported events to determine the outcome (ie, record stop dates or confirm if they are still continuing) and record as described in [Section 10.3](#), and record concomitant medications used to treat NDCMCs and SAEs.
- Measure and record the participant's axillary temperature (°C).
- Prior to vaccination, collect a blood sample of approximately 5 mL for immunogenicity (a topical anesthetic is permitted).
- Unblinded site staff will administer a single 0.5-mL injection of 20vPnC or 13vPnC into the anterolateral thigh (preferably into the left anterolateral thigh). (NOTE: A **blinded** site staff **should not** open a carton of the investigational product in order to maintain the blind).
- The site staff (either blinded or unblinded) will administer concomitant vaccines containing Hib, diphtheria, tetanus, acellular pertussis, poliovirus, measles, rubella, and varicella antigens and other permitted vaccines into the upper arm(s). A blinded staff member will record the site of administration on the CRF.

After vaccination:

- Blinded site staff will observe the participant for 30 minutes after vaccination for any reactions. Record any AEs on the CRF and on an SAE form as applicable. Record concomitant medications used to treat SAEs and NDCMCs.
- Issue the participant's parent(s)/legal guardian(s) an e-diary (device or application). Provide instructions on use and completion of the e-diary. Ask the participant's parent(s)/legal guardian(s) to complete the e-diary from Day 1 to Day 7, with Day 1 being the day of vaccination.
- Ask the participant's parent(s)/legal guardian(s) to contact the investigator site staff or investigator as soon as possible during the 7-day postvaccination period if the participant has a fever  $>40.0^{\circ}\text{C}$ , redness and/or swelling at the 20vPnC or 13vPnC injection site measuring  $>14$  measuring device units ( $>7$  cm), or severe 20vPnC or 13vPnC injection site pain (causes limitation of limb movement), to determine if the event requires further assessment by the investigator.
- Remind the participant's parent(s)/legal guardian(s) to contact the investigator or investigator site staff as soon as possible if any significant illness or medical event (eg, emergency room visit or hospitalization) occurs during the study period.
- Confirm whether the participant's parent(s)/legal guardian(s) still possesses the participant contact card. Provide a participant contact card if needed.
- Remind the participant's parent(s)/legal guardian(s) that the use of prophylactic antipyretic/pain medication, while permitted, is not recommended on the day of investigational product administration (before or after vaccination).
- The investigator or an authorized designee completes the CRF and the source documents and updates the investigational product accountability records.
- The investigator or appropriately qualified designee reviews the e-diary data online at frequent intervals for the 7 days following vaccination to evaluate participant compliance and as part of the ongoing safety review.

**8.11.6. Visit 6 (Dose 4 Follow-up Visit, 28 to 42 Days After Visit 5 [Dose 4])**

- Ensure and document that the participant continues to be eligible for the study (see [Section 7.2](#) for participant discontinuation/withdrawal) and none of the temporary delay criteria are met ([Section 5.5](#)).
- Record nonstudy vaccinations administered since Visit 5, as described in [Section 6.5](#).

- Review the participant's e-diary data with the participant's parent(s)/legal guardian(s); collect stop dates of any e-diary events ongoing on the last day that the e-diary was completed and record stop dates in the CRF.
- Collect the e-diary (if device provided).
- Determine whether any AEs (includes nonserious AEs, SAEs, and NDCMCs) have occurred since the previous visit and follow up on any previously reported events to determine the outcome (ie, record stop dates or confirm if they are still continuing) and record as described in [Section 10.3](#), and record concomitant medications used to treat NDCMCs and SAEs.
- Collect a blood sample of approximately 5 mL for immunogenicity (a topical anesthetic is permitted).
- The investigator or an authorized designee completes the CRF and the source documents.

#### **8.11.7. Unscheduled Visits**

If the participant's parent(s)/legal guardian(s) reports redness or swelling at the injection site measuring >14 measuring device units (>7 cm), severe injection site pain, or a fever >40.0°C during the 7-day postvaccination period, a telephone contact must occur as soon as possible between the investigator or medically qualified designee and the participant's parent(s)/legal guardian(s) to assess if an unscheduled investigator site visit is required. Note that for a fever >40.0°C, the participant's parent(s)/legal guardian(s) should be instructed not to delay seeking medical care, as appropriate, while arranging for an unscheduled visit if applicable. A visit should be scheduled as soon as possible to assess the extent of the injection site reaction, unless any of the following is true:

- The participant's parent(s)/legal guardian(s) is unable to bring the participant to the unscheduled visit.
- The reaction is no longer present at the time of the telephone contact.
- The participant's parent(s)/legal guardian(s) recorded an incorrect value in the e-diary (confirmation of an e-diary data entry error).
- The principal investigator (PI) or authorized designee determined it was not needed.

This telephone contact will be recorded in the participant's source documentation and the CRF.

If the participant's parent(s)/legal guardian(s) is unable to bring the participant to an unscheduled visit, or the PI or authorized designee determined it was not needed, any ongoing reactions must be assessed at the next study visit.

During the investigator site visit, the reactions should be assessed by the investigator or a medically qualified member of the study staff such as a study physician or a study nurse, as applicable to the investigator's local practice, who will:

- Measure axillary temperature (°C).
- Measure minimum and maximum diameters of redness (if present).
- Measure minimum and maximum diameters of swelling (if present).
- Assess injection site pain in accordance with the grades provided in [Section 8.2.2](#) (if present).
- Assess other findings associated with the reaction and record on the AE page of the CRF, if appropriate.

The investigator or an authorized designee will complete the unscheduled visit assessment page of the CRF.

The participant's parent(s)/legal guardian(s) will also be instructed to contact investigator site staff if the participant experiences any emergency room visit or hospitalization for decreased appetite, drowsiness/increased sleep, irritability, or local reaction within 7 days of vaccination.

The participant's parent(s)/legal guardian(s) will also be instructed to contact the investigator site to report any significant illness, medical event, or hospitalization that occurs during the study period. The investigator site should determine if an unscheduled visit to further evaluate the event is warranted in all such cases.

Additionally, study staff may contact the participant's parent(s)/legal guardian(s) to obtain additional information on Grade 3 events entered into the e-diary.

## 9. STATISTICAL CONSIDERATIONS

Methodology for summary and statistical analyses of the data collected in this study is described here and further detailed in a SAP, which will be maintained by the sponsor. The SAP may modify what is outlined in the protocol where appropriate; however, any major modifications of the primary endpoint definitions or their analyses will also be reflected in a protocol amendment.

### 9.1. Estimands and Statistical Hypotheses

#### 9.1.1. Estimands

The estimands corresponding to each of the primary, secondary CCI objectives is described in the table in [Section 3](#). The estimands to evaluate the immunogenicity objectives for noninferiority are based on evaluable populations ([Section 9.3](#)). These estimands estimate the vaccine effect in the hypothetical setting where participants follow the study

schedules and protocol requirements as directed. The estimand addresses the objective of estimating the maximum potential difference between the 2 compared groups, since the impact of noncompliance is likely to diminish the observed difference between the 2 groups. Missing serology results will not be imputed. Immunogenicity results that are below the LLOQ will be set to 0.5 x LLOQ in the analysis.

In the primary safety objective evaluations, missing e-diary data will not be imputed. Missing AE dates will be imputed according to Pfizer safety rules. No other missing information will be imputed in the safety analysis.

### 9.1.2. Statistical Hypotheses

Noninferiority of the immune response at 1 month after Dose 3 for each serotype in 20vPnC is evaluated by the percentage of participants with predefined pneumococcal serotype-specific IgG concentrations based on results from the 20vPnC SC group and the 13vPnC SC group as below. The noninferiority for the immune response at 1 month after Dose 3 for a serotype will be declared if the null hypotheses ( $H_0$ ) is rejected at the 0.05 level.

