#### 9.1.2.1. Noninferiority Comparing Percentage of Participants with Predefined Pneumococcal Serotype-Specific IgG Concentrations 1 Month after Dose 3 (Primary Endpoint)

Hypothesis testing will be used to assess noninferiority of 20vPnC SC to 13vPnC SC by the percentage of participants with predefined pneumococcal serotype-specific IgG concentrations 1 month after Dose 3. The null hypothesis ( $H_{0A}$ ) for each serotype is

$$H_{0A}: \pi_{20vPnC\ SC} - \pi_{13vPnC\ SC} \leq -10\%,$$

with a 10% margin for noninferiority, where

- $\pi_{20vPnC\ SC}$  is the percentage of participants achieving an IgG antibody concentration of a predetermined level in the 20vPnC SC group from the serotype 1 month after Dose 3;
- If the serotype is from the 13 matched serotypes (1, 3, 4, 5, 6A, 6B, 7F, 9V, 14, 18C, 19A, 19F, 23F),  $\pi_{13vPnC\ SC}$  is the percentage of participants achieving a predefined IgG concentration level for the serotype from the 13vPnC SC group 1 month after Dose 3;
- If the serotype is from the 7 additional serotypes (8, 10A, 11A, 12F, 15B, 22F, 33F) in 20vPnC,  $\pi_{13vPnC\ SC}$  is the percentage of participants achieving a predefined IgG concentration level from the serotype with the lowest percentage 1 month after Dose 3 among the 13 serotypes from the 13vPnC SC group, provided that the lowest percentage is not from serotype 3. If the lowest percentage in the 13vPnC SC group is from serotype 3, the next lowest percentage in the 13vPnC SC group will be used in the comparison. Historical data suggest that serotype 3 behaves somewhat differently from the other serotypes in 13vPnC; therefore, IgG results from serotype 3 will not be used in the comparison to assess the noninferiority of the 7 additional serotypes.

- The predefined levels for serotype-specific IgG concentrations are 0.35 µg/mL for all serotypes in 20vPnC except that the predefined levels are 0.23 µg/mL, 0.10 µg/mL, and 0.12 µg/mL for serotypes 5, 6B, and 19A, respectively.

The null hypothesis  $H_{0A}$  will be rejected and noninferiority of 20vPnC SC to 13vPnC SC for the percentage of participants with predefined IgG concentration level will be declared for a serotype if the lower bound of the 2-sided 95% CI for the difference (20vPnC SC group – 13vPnC SC group) in percentages, computed using the Miettinen and Nurminen method, is greater than –10% (10% noninferiority margin).

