#### **9.1.2.2. Noninferiority Comparing Pneumococcal Serotype-Specific IgG Concentrations 1 Month after Dose 3 (Secondary Endpoint)**

Hypothesis testing will be used to assess noninferiority of 20vPnC SC to 13vPnC SC for pneumococcal serotype-specific IgG GMCs 1 month after Dose 3. The null hypothesis ( $H_{0B}$ ) for each serotype is

$$H_{0B}: \ln(\mu_{20vPnC\ SC}) - \ln(\mu_{13vPnC\ SC}) \leq \ln(0.5)$$

where  $\ln(0.5)$  corresponds to a 2-fold margin for noninferiority and

- $\ln(\mu_{20vPnC\ SC})$  is the natural log of the IgG GMC in the 20vPnC SC group for that serotype 1 month after Dose 3;
- If the serotype is from the 13 matched serotypes (1, 3, 4, 5, 6A, 6B, 7F, 9V, 14, 18C, 19A, 19F, 23F),  $\ln(\mu_{13vPnC\ SC})$  is the natural log of the IgG GMC in the 13vPnC SC group 1 month after Dose 3;
- If the serotype is from the 7 additional serotypes (8, 10A, 11A, 12F, 15B, 22F, 33F) in 20vPnC,  $\ln(\mu_{13vPnC\ SC})$  is the natural log of the IgG GMC for the serotype with the lowest IgG GMC 1 month after Dose 3 among the 13 serotypes from the 13vPnC SC group, provided that the lowest GMC is not from serotype 3. If the lowest GMC in the 13vPnC SC group is from serotype 3, the next lowest GMC in the 13vPnC SC group will be used in the comparison. As stated in [Section 9.1.2.1](#), historical data suggest that serotype 3 behaves somewhat differently from the other serotypes in 13vPnC; therefore, IgG results from serotype 3 will not be used in the comparison to assess the noninferiority of the 7 additional serotypes.

The null hypothesis  $H_{0B}$  will be rejected and noninferiority of 20vPnC SC to 13vPnC SC for the serotype-specific IgG GMC will be declared for a serotype if the lower bound of the 2-sided 95% CI for GMR of serotype-specific IgG GMCs (20vPnC SC group over 13vPnC SC group) is greater than 0.5 (2-fold margin).

CCI [Redacted]

[Redacted]	[Redacted]	[Redacted]	[Redacted]	[Redacted]
[Redacted]	[Redacted]	[Redacted]	[Redacted]	[Redacted]
[Redacted]	[Redacted]	[Redacted]	[Redacted]	[Redacted]
[Redacted]	[Redacted]	[Redacted]	[Redacted]	[Redacted]
[Redacted]	[Redacted]	[Redacted]	[Redacted]	[Redacted]
[Redacted]	[Redacted]	[Redacted]	[Redacted]	[Redacted]
[Redacted]	[Redacted]	[Redacted]	[Redacted]	[Redacted]
[Redacted]	[Redacted]	[Redacted]	[Redacted]	[Redacted]
[Redacted]	[Redacted]	[Redacted]	[Redacted]	[Redacted]
[Redacted]	[Redacted]	[Redacted]	[Redacted]	[Redacted]

CCI [Redacted]  
 CCI [Redacted]  
 CCI [Redacted]

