**Table 6. Sample Size and Power to Demonstrate Noninferiority Comparing Serotype-Specific IgG Concentrations From 20vPnC SC Group to 13vPnC SC Group with the Specified Criteria**

Evaluable Sample Size per Group	Power (%) to Demonstrate Noninferiority of Serotype-Specific IgG Concentrations for all 20 Serotypes a
150	82
180	89
200	92

Note: Power is estimated by 5,000 simulations.

- a. Noninferiority for each serotype is defined by the lower bound of the 2-sided 95% CI for difference (20vPnC SC – 13vPnC SC) in percentage of participants with specified threshold above -10%, calculated with Miettinen and Nurminen method.

CCI [Redacted]

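### Is the 0.05 level stated for noninferiority twice the level that the confidence-interval rule applies?

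*Protocol*

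**What the plan says.** Protocol 9.1.2 introduces the noninferiority hypotheses and says noninferiority for a serotype is declared if the null "is rejected at the 0.05 level". It gives no sidedness, and it points forward to the subsections that follow.

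Those subsections say what rejection means:

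- **Primary (9.1.2.1).** The null is a difference of −10 percentage points or worse, "with a 10% margin for noninferiority, where" the terms are then defined. Noninferiority "will be declared for a serotype if the lower bound of the 2-sided 95% CI for the difference", by the Miettinen and Nurminen method, lies above −10%.
- **Secondary (9.1.2.2).** The null is a log ratio of ln(0.5) or less. It is rejected if the lower bound of the 2-sided 95% CI for the geometric mean ratio "is greater than 0.5 (2-fold margin").
- **Power (Table 6).** Footnote a reads: "Noninferiority for each serotype is defined by the lower bound of the 2-sided 95% CI for difference" above −10%. The table note adds: "Power is estimated by 5,000 simulations".

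The synopsis (Statistical Methods) and SAP 5.1.1.1 and 5.1.1.2 give the same rule. Protocol 9.4 and SAP 5.2 set all confidence intervals at two-sided 95%. The SAP hypothesis sections do not repeat the 0.05 wording.

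**The concern.** Both nulls have a single direction of rejection. The level of a test is normally its largest rejection probability under its own null, so a reader could take 0.05 as the size of a one-sided test. Such a test would use the lower bound of a 90% CI. The subsections prescribe a 95% CI, whose lower bound gives a one-sided size of 0.025. On that reading the general statement and the detailed rule differ by a factor of two.

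This would matter if the text really allowed both. Alpha is a central figure of the pivotal comparison. The synopsis requires, in principle, noninferiority on all 20 serotypes, so one borderline serotype could decide the result. A serotype whose test statistic falls between the two critical values would pass under one rule and fail under the other.

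**Working it through.** **Inputs.** Stated level 0.05, sidedness not given (Protocol 9.1.2). Margin −10 points and lower bound of a 2-sided 95% Miettinen-Nurminen CI (9.1.2.1). Target of 200 evaluable participants per group (4.1.2). The response rates assumed for Table 6 are blacked out, so control rates of 80% to 98% are used below as an illustrative range.

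**Step 1: reproduce the stated 0.05.** The lower bound of a 2-sided 95% CI uses z = 1.960.

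- One-tail area: 1 − Φ(1.960) = 0.025.
- Two-tail area: 2 × 0.025 = 0.050.

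The stated figure is reproduced on the two-sided reading. A one-sided test at 0.05 would use z = 1.645, the critical value for a 90% CI.

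**Step 2: how far apart the two rules are.** The test statistic at the margin is

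z = (p₂₀ − p₁₃ + 0.10) / √{[p̃₂₀(1 − p̃₂₀)/n + p̃₁₃(1 − p̃₁₃)/n] × N/(N − 1)},

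where the p̃ are the maximum-likelihood rates constrained to differ by −0.10, n = 200 and N = 400. Summing exact binomial probabilities over all outcomes with z above the critical value gives:

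| Control rate | False-pass rate at the margin, 95% CI | False-pass rate at the margin, 90% CI | Power at equal rates, 95% CI | Power at equal rates, 90% CI |
|---|---|---|---|---|
| 80% | 0.0251 | 0.0501 | 70.2% | 80.2% |
| 85% | 0.0250 | 0.0497 | 79.1% | 87.1% |
| 90% | 0.0245 | 0.0489 | 90.0% | 94.8% |
| 95% | 0.0230 | 0.0490 | 98.9% | 99.6% |
| 98% | 0.0223 | 0.0475 | >99.9% | 100.0% |

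Power is for a single serotype.

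**Step 3: a borderline case.** Take 172/200 (86%) against 180/200 (90%), a difference of −4 points. At the margin z = 1.80, which lies between 1.645 and 1.960. The lower bound is −10.55% with a 95% CI (fails) and −9.46% with a 90% CI (passes).

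**Step 4: which rule the documents contain.**

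| Place | Rule given |
|---|---|
| Protocol synopsis, Statistical Methods | lower bound, 2-sided 95% CI |
| Protocol 9.1.2 | 0.05 level, no sidedness |
| Protocol 9.1.2.1 and 9.1.2.2 | lower bound, 2-sided 95% CI |
| Protocol Table 6, footnote a | lower bound, 2-sided 95% CI |
| Protocol 9.4 | all CIs two-sided 95% |
| SAP 5.1.1.1 and 5.1.1.2 | lower bound, 2-sided 95% CI |
| SAP 5.2 | all CIs two-sided 95% |

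No entry gives a 90% CI or a one-sided 0.05 level. The one unlabelled entry agrees with all the others once it is read as two-sided. The case in step 3 therefore has one outcome under this plan: that serotype fails.

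**Step 5: power.** Table 6 (82%, 89% and 92% at 150, 180 and 200 per group) cannot be recomputed without the blacked-out rates. Its footnote names the 95% CI rule, so the stated power and the decision rule rest on the same test.

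**The case for a change.** The best argument for a change is that the sentence in 9.1.2 is itself a declaration rule, in the section that sets up the pivotal comparison, and that a null with one rejection direction has no natural two-sided level. The SAP gives the interval rule without stating an alpha, so it does not supply the missing word. A label would cost one line and would guard against someone misreporting the trial's alpha.

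Part of this stands. The nulls are one-sided, the rule has a one-sided size of 0.025, and 9.1.2 does not say which convention its 0.05 follows. The arithmetic in the comparison is also sound.

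The claim of a doubled alpha does not stand, because it depends on the word one-sided, which the protocol does not use. Nor does the risk of opposite verdicts. An analyst does not have to infer the critical value from 0.05, because the next two subsections state when each null is rejected, and the SAP repeats them. The 95% rule is also the stricter of the two, so any serotype that passes it would pass a one-sided 0.05 test as well.

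Protocol 9.1.3 (multiplicity) appears in the contents, but its text is not in the public version. It may or may not state the sidedness, and it is counted for neither side.

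**Conclusion.** The concern does not hold as a discrepancy in alpha. The plan has one operative rule, the lower bound of a 2-sided 95% CI against the margin. That is 0.05 two-sided, or 0.025 one-sided. Section 9.1.2 omits the label, and analysts will fill the gap correctly from the text directly below it.

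The effect on the trial is nil: no confidence interval, sample size, power figure or serotype verdict would change if the label were added. The differences in the working (about 2.2% to 2.5% against 4.8% to 5.0% for the false-pass rate, and up to 10 points of single-serotype power) compare the plan with a rule it never proposes.

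This rests on the text that can be read in both documents. The control rates are illustrative and affect only the size of that comparison, not the conclusion.
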